9.4.4 End of infusion PK concentration vs VAS correlation

Correlation between End of Infusion PK Concentration vs Increase in Pain Score (VAS) from Week 1 to Week 12 will be assessed graphically by means of linear regression analysis where VAS and EoI PK concentration will be considered as dependent and independent variables, respectively. Linear regression parameters, correlation estimate and their 95% confidence intervals will be presented.

9.5 Pharmacodynamics

Plasma samples collected, at Week 1 and Week 12 pre and post-dose (around the Tmax for the post-dose measurement), from all subjects, will be used for exploratory pharmacodynamic (PD) assessment by using an in vitro test to assess the propensity for hydroxyapatite (HAP) crystal formation in plasma (see Protocol CT2015-04.2).

9.5.1 % PD Inhibition

The PD assessment will be performed by Laboratoris Sanifit and sent to [REDACTED] for analysis. The readout of the assay is a % inhibition of the propensity for hydroxyapatite crystal formation per each subject and visit.

The percent inhibition of HAP crystallization will be summarized by visit. In addition, the same information will be listed by all subjects and all timepoints together with the PK.

9.5.2 % PD Inhibition vs BWAT correlation

Correlation between % PD Inhibition vs Increase in BWAT Total Score from Week 1 to Week 12 will be assessed graphically by means of linear regression analysis where BWAT and % PD Inhibition will be considered as dependent and independent variables, respectively. Linear regression parameters, correlation estimate and their 95% confidence intervals will be presented.

9.5.3 % PD Inhibition vs VAS correlation

Correlation between % PD Inhibition vs Increase in Pain Score (VAS) from Week 1 to Week 12 will be assessed graphically by means of linear regression analysis where VAS and % PD Inhibition will be considered as dependent and independent variables, respectively. Linear regression parameters, correlation estimate and their 95% confidence intervals will be presented.

9.6 PK/PD modelling

PK/PD modeling links the drug plasma concentration with an efficacy metric, and it is performed to guide in the design for future studies.

The % inhibition of HAP crystallization and the Cmax will be used to calculate a PK/PD correlation between both parameters at Week 1, Week 12 and combining both visits.

9.7 Subgroup analysis

Subgroup analysis will be summarized for the ITT analysis set. Subgroups will be based on baseline and demographic categories including age (e.g., < 65 years of age and \geq 65 years of age), gender, race, and country, and use of STS (sodium thiosulfate).

9.7.1 BWAT

Subgroup analysis will be done for the absolute change in BWAT total score between baseline (Week 1) and Week 12 for the primary lesion as specified in Section 8.3. Missing imputation will be done as specified in Section 9.2.1.

9.7.2 VAS

Subgroup analysis will be done for the absolute change in VAS total score between Week 1 and Week 12 as specified in Section 8.3. Missing imputation will be done as specified in Section 9.2.2.4.

VAS responder analysis for STS subgroup will be done by each imputation method summarizing the percentage of reduction of VAS from Week 1 to Week 12 (Shell T-8). Percentage of reduction will be calculated as follows:

$$\text{Percentage of reduction} = -100 * (\text{Week 12 VAS score} - \text{Week 1 VAS score}) / (\text{Week 1 VAS score})$$

The following categories will be used:

- Worsening (negative percentage of reduction)
- ≥ 0 and < 30
- ≥ 30
- % not available (Week 1 VAS score = 0)
- Missing W12 value

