### 5.3. Inclusion Criteria

Patients who meet the following criteria will be considered eligible to participate in the clinical trial:

1. Patients with either newly diagnosed CUA OR recurrent CUA that has been dormant with no skin lesion involvement for at least 90 days from study start (new or recurrent diagnosis must be made within 5 weeks of study start)
2. Patients who signed the written informed consent to participate in this clinical trial (prior to any clinical trial-related procedures being performed), after reading the Patient Information Sheet and Informed Consent Form (ICF), and who had the opportunity to discuss the clinical trial with the Investigator or designee
3. Males or females aged  $\geq 18$
4. Patients on maintenance haemodialysis
5. Patients with at least a minimum level of pain on VAS scale or on pain-killers stronger than NSAIDs

6. Females of child-bearing potential should use a highly effective contraceptive measure throughout the study AND have a negative serum pregnancy test at entry. Male patients having sexual relationship in which pregnancy can occur should take adequate contraceptive precautions (wear a condom) (see Section 8.3.1.)

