### 7.5.1. Pain Score -VAS

The Visual Analogue Scale (VAS) will be used to assess pain, as per the patient. A VAS is a measurement instrument that aims to measure a characteristic or attitude that is believed to range across a continuum of values and cannot easily be directly measured. For example, the amount of pain that a patient feels ranges across a continuum from none to an extreme amount of pain.

Operationally, a VAS is usually a horizontal line, 100 mm in length, anchored by word descriptors at each end, as illustrated in

[figure not shown]

Figure 4 The patient marks on the line the point that he feels represents his perception of his current status. The VAS score is determined by measuring in millimetres from the left hand end of the line to the point that the patient marks [51].

[figure not shown]

Figure 4: VAS Analogue Scale

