9.2.2 Secondary endpoints

9.2.2.1 *Change from baseline in BWAT total and component scores by visit*

BWAT Score is collected at Week 1, Week 2, Week 4, Week 6, Week 8, Week 10, Week 12 and Follow-up. Differences in absolute and relative change from baseline will be also presented. Differences from baseline will be tested using a Paired Student's T-Test. (Shell T-7). Additionally, a figure presenting the evolution (mean, and 95% confidence interval) of the total score and

individual items by visit will be presented (Shell F-2). This analysis will be done using Observed Cases.

9.2.2.2 *The previous analysis will also be done for the secondary and tertiary lesions if there is enough data. Change from baseline in imaging score by visit*

Image evaluation will be summarized separately for the blinded and unblinded reviews. Percentages for each category and their exact 95% confidence interval (Clopper-Pearson) will be presented. Imputation methods will not be used for this score.

9.2.2.3 *Change from baseline in the Pain Visual Analog Scale (VAS) by visit*

Absolute change from baseline will be calculated as differences in the total score from Week 1 to Week 12. Descriptive statistics will be presented. Differences between the two visits will be analyzed using a Paired Student's T-Test. (Shell T-7)

The Week 1 to Week 12 analysis will be done using Multiple Imputation, and supported by the different sensitivity analysis as specified in Section 8.4. A forest plot summarizing these results will be produced presenting the estimated change from baseline and 95% confidence interval for the different imputation methods. These analysis will also be done for the PP population.

Additionally, the VAS Score is collected at Screening, Week 1, Week 2, Week 4, Week 6, Week 8, Week 10, Week 12 and Follow-up. VAS scores will be summarized by visit. Differences in absolute and relative change from Week 1 to each visit will be presented descriptively. Finally, differences in absolute change from Week 12 to Follow-up will be summarized. Statistically significant differences from the reference values will be tested using a Paired Student's T-Test (Shell T-7). Additionally, a figure presenting the evolution (mean, and 95% confidence interval) of the VAS score by visit will be presented (Shell F-2). This analysis will be done using Observed Cases.

9.2.2.4 *Change from baseline in total and subscales of wound QoL score by visit*

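### In the VAS responder table for the STS subgroup, a rise in pain from a Week 1 score of 0 is not counted as worsening, so the Worsening row can be undercounted

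*SAP*

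**What the plan says.** SAP 9.7.2 plans a VAS responder analysis for the STS subgroup, run under each imputation method and "summarizing the percentage of reduction of VAS from Week 1 to Week 12". After the words "Percentage of reduction will be calculated as follows" it gives −100 × (W12 − W1) / W1, where W1 and W12 are the Week 1 and Week 12 scores. The table has five rows:

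- "Worsening (negative percentage of reduction")
- a reduction of at least 0 and below 30
- a reduction of 30 or more
- "not available (Week 1 VAS score = 0")
- "Missing W12 value"

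The zero-score row is not split by the Week 12 value, and I found no rule elsewhere that reclassifies these patients.

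Protocol 5.3, criterion 5, admits "Patients with at least a minimum level of pain on VAS scale or on pain-killers stronger than NSAIDs". Protocol 7.5.1 describes a 100 mm line and states: "The VAS score is determined by measuring in millimetres from the left hand end of the line".

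The main VAS analysis in SAP 9.2.2.3 uses a different measure: "Absolute change from baseline will be calculated as differences in the total score from Week 1 to Week 12". The VAS subgroup comparison that opens SAP 9.7.2 also uses absolute change.

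**The concern.** When W1 is 0 the percentage cannot be computed, but the direction of change can still be seen. The Worsening row requires a computable percentage, so it cannot receive a patient whose pain started at zero and rose. The table then treats a 1 mm rise from 1 mm as worsening, and a rise across the whole scale from zero as information that is not available.

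The error runs one way. A patient at the floor can only stay there or get worse, so the row can hide worsening but never improvement. Someone who reports no pain while taking strong analgesics is also a patient whose pain control could fail. SAP section 10 drops the planned continuous analysis of analgesic change, so fewer analyses remain that would show such a failure. Anyone who reads only the responder table could see too few worsened patients.

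**Working it through.** The plan states no figure for this table, so there is none to reproduce. The check applies the SAP 9.7.2 formula and rows to test pairs and then sizes the effect.

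**Inputs.** The formula and rows are from SAP 9.7.2, the 0 to 100 mm scale from Protocol 7.5.1, and the entry rule from Protocol 5.3. The table size of 15 is the planned number of patients (Protocol 9.5; SAP 6.1 says up to 15). The number of patients with W1 = 0 and W12 > 0, called k, is not in the documents; I assume 0 to 3.

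**Step 1: can W1 be 0?** Criterion 5 has two branches joined by an or. The analgesic branch sets no minimum VAS, so a score of 0 is admissible. VAS is also measured at both Screening and Week 1, so a patient with some pain at Screening could score 0 at Week 1.

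**Step 2: where do patients fall?**

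| W1 (mm) | W12 (mm) | Change (mm) | Percentage reduction | Row under the SAP |
|---|---|---|---|---|
| 0 | 0 | 0 | undefined | not available |
| 0 | 1 | +1 | undefined | not available |
| 0 | 50 | +50 | undefined | not available |
| 0 | 100 | +100 | undefined | not available |
| 1 | 2 | +1 | −100 × 1/1 = −100 | Worsening |
| 50 | 60 | +10 | −100 × 10/50 = −20 | Worsening |
| 50 | 50 | 0 | 0 | ≥0 and <30 |
| 50 | 30 | −20 | −100 × (−20)/50 = 40 | ≥30 |

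**Step 3: size.** With all n patients in the denominator, the Worsening row is too low by k/n. For n = 15:

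- k = 0: 0 points
- k = 1: 1/15 = 6.7 points
- k = 2: 2/15 = 13.3 points
- k = 3: 3/15 = 20.0 points

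If 3 other patients worsen (assumed), the SAP table shows 3/15 = 20.0% in every case. The proportion whose pain rose is 20.0%, 26.7%, 33.3% or 40.0% for k = 0, 1, 2 or 3.

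A table for the STS subgroup will usually have a smaller n. One such patient is 10 points when n = 10 and 20 points when n = 5 (both sizes assumed). At n = 2, the smallest category SAP 8.3 allows, one patient is 50 points.

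**Step 4: the ≥30 row.** A patient with W1 = 0 can never enter this row, before or after any reclassification. With the full set as denominator, its percentage does not change.

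**Step 5: the denominator.** SAP 8.1 allows percentages out of the analysis set or out of the non-missing sample, as appropriate, and SAP 9.7.2 does not choose. Suppose 6 of 15 patients reach ≥30 and 2 have W1 = 0 (assumed). Then 6/15 = 40.0% would become 6/13 = 46.2% if those 2 left the denominator. With 3 patients in the Worsening row, the SAP table would show 3/13 = 23.1%. The correct value is 5/15 = 33.3% if both zero-score patients rose, and 3/15 = 20.0% if both stayed at zero. So the number in the Worsening row can only be too low, but the direction of error in its percentage is certain only with the full denominator.

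**The case against.** The case for leaving the table alone is that an undefined percentage reported as not available is a transparent convention. The patients stay in the table, in a row whose label gives the reason. A rise from zero is counted in full in the main VAS analysis and in the STS comparison of absolute change, and VAS is also summarised by visit and listed by patient. The affected table is descriptive, no test or decision rule is attached to it, and the SAP describes the study as exploratory and proof of concept. All of that stands, and it makes the point a small one.

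A reader might infer that a Week 1 score of 0 is to be expected. The documents show only that it is possible. Protocol 4.1 points the other way, since its diagnostic features call for painful ulcers and it describes intense pain as the primary manifestation. The number affected could be none.

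A reader might also infer that the responder result is biased in favour of treatment. That would need the zero-score patients to leave the denominator, which SAP 8.1 leaves open but nowhere states; the layout of Shell T-8 is not in the text available.

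Nor should the row simply be deleted. Placing a patient with no pain on either occasion in the ≥0 and <30 row would present someone who could not improve as a weak responder. None of this explains why a known rise in pain should stay out of the Worsening row.

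**Conclusion.** The gap is real and minor. Under SAP 9.7.2, a patient with W1 = 0 and a higher W12 is shown as not available, so the number in the Worsening row can be too low and never too high. With the full denominator the understatement is 0 to 20 percentage points for an assumed 0 to 3 such patients in a table of 15, and more in a smaller STS subgroup. If no patient scores 0 at Week 1 and then rises, there is no effect.

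The finding covers this one subgroup table. It does not reach the absolute-change VAS results, and it does not reach the ≥30 row if percentages are taken over the full analysis set.

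**What to change.** In SAP 9.7.2 and Shell T-8:

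- Count W1 = 0 with W12 > 0 as Worsening, or show it as a separate row for patients who worsened from zero and add that row to the worsening total.
- Keep a labelled row for W1 = 0 with W12 = 0, where no reduction was possible.
- Use the full analysis set as the denominator for every row.
- State which row takes a patient with W1 = 0 and a missing W12, since two rows now fit.

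This is a short edit to the text and the shell and needs no new data. The small cost is that the Worsening row then rests on the sign of the absolute change for these patients and on the percentage for the others; a footnote can say so.

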10. SUMMARY OF CHANGES FROM THE PROTOCOL

5.2 The protocol did not provide details about the methods used for the analysis of the study endpoints, nor at which timepoints. The primary endpoint was assessed comparing Week 1 to Week 12. Whereas, secondary endpoints were assessed comparing baseline to all subsequent visits. Differences from baseline were tested using a Paired Student's T-Test. Last Observation Carried Forward (LOCF) and Multiple Imputation (MI) was used to treat missing data.

5.2.2 "Change in dose and type of pain medication assessed as a continuous variable. Name (INN), dose, and number of pills captured" was not done but the use of pain medications will be discussed in the CSR.

6.3.3 Criteria for subject withdrawal - For criteria for withdrawal, data are presented for subjects who received at least one dose of study medication. Subjects who did not meet entry criteria are presented as screen failures.

8.2.2 Efficacy Analysis Set. The efficacy analysis set has been divided in Intention to Treat and Per Protocol sets.

12. APPENDICES

The appendices contain a list of Tables, Figures, and Listings to be produced, as well as their corresponding shells.
